### 7.7.2. Objective 2: 2-Year Non-Inferiority

Bayesian simulations were performed to evaluate the operating characteristics for testing the Objective 2 non-inferiority hypothesis. In the pivotal IDE study, 135 of 204 patients (66.2%) achieved Month 24 CCS. These results were used to define the prior distribution for coflex® in conjunction with surgical decompression as beta (135.5, 69.5) since the distribution prior to the IDE trial was specified as beta (0.5, 0.5). This Jeffries non-informative prior was assumed for patients undergoing decompression alone. A non-inferiority margin of -0.10 is specified. Non-inferiority will be concluded if the Bayesian posterior probability that ( $CCS_{coflex+decomp.} - CCS_{decomp.} > -0.10$ ) is at least equal to 0.95. When evaluating statistical power, it was assumed that the true success rate 0.662 for patients treated with coflex®. However, preliminary results from the German decompression study suggest some an advantage of coflex® over decompression alone. Therefore, when evaluating power, Month 24 CCS for decompression alone was assumed to be at least 2% lower, or 0.642. In contrast, Type 1 error was evaluated by assuming that the coflex® success rate 0.662 but that the success rate for decompression was 0.10 larger. With N=150 patients per group, power was shown to be 89%; and type 1 error was shown to be 0.042 and 0.052 'prior to the prior' and with the prior engaged, respectively.

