--	---

statistical power, it was assumed that the true success rate 0.662 for patients treated with coflex®. However, preliminary results from the German decompression study suggest some an advantage of coflex® over decompression alone. Therefore, when evaluating power, Month 24 CCS for decompression alone was assumed to be at least 2% lower, or 0.642. In contrast, Type 1 error was evaluated by assuming that the coflex® success rate was 0.662 but that the success rate for decompression was 0.10 larger. With N=150 patients per group, power was shown to be 89%; and type 1 error was shown to be 0.042 and 0.052 'prior to the prior' and with the prior engaged, respectively.

**Objective 3: (two-year superiority)** Superiority will be evaluated by determining the Bayesian posterior probability that  $(CCS_{coflex+decomp.} - CCS_{decomp.}) > 0$ . Ho will be rejected in favor of Ha if the Bayesian posterior probability is at least equal to 0.95. The same prior distributions that will be used in Objective 2 will be used in the evaluation this posterior probability. The expected device group difference in Month 24 CCS between coflex® and decompression alone was evaluated based on results from an administrative analysis of the ongoing PAS being conducted in Germany. The device group difference in Month 24 overall success was 12.5% (95% CI -3.5% to 28.4%) based on a simplified CCS that incorporated reoperations, lumber injections, and ODI improvements. Bayesian simulations demonstrate that when assuming the same superiority, with N=150 patients per group will result in 88% statistical power to demonstrate superiority. Type 1 error is controlled at <0.05 'prior to prior' and with prior for coflex® engaged. If the true difference is only 10%, then power is reduced to 73%.

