### 7.7.1. Objective 1: 5-Year Superiority

These simulations were used to evaluate the power and type 1 error for determining superiority of coflex in conjunction with surgical decompression relative to surgical decompression alone at Month 60. For the purpose of these simulations it was assumed that the Month 60 success rate would be 0.57 for coflex®. The prior distribution derived in the Memo is beta(82.1,62.1) reflecting a 20% discount off of a total prior sample size of N=179. Power was found to be equal to 83% if the true superiority margin is 12.5%. If the true superiority margin is only 10%, then power to conclude superiority is reduced to 65%. Type 1 error was determined through simulation by assuming that the probabilities of Month 60 success were equal to 0.57 for both treatment groups. The estimated type 1 error rate is equal to 0.037(SD=0.0011) based on an average of 10 identical simulations with varying randomization seeds.

It may be now be noted that subsequent to the Bayesian design memo submission, the final results from the PMA study were submitted to FDA in the Final Report (P110008/R014). The Month 60 PAS CCS was achieved in 55.9% (104/186) patients which is very close to the projected success rate of 57%. The total sample size of 186 is slightly larger than the assumed 179 which implies a discount of the prior of 23% rather than 20%. Sensitivity analyses (see Table 4 from Bayesian Memo) were provided that demonstrate that type 1 error is 0.040, still below 0.05, if the true success rate is 56% rather than 57%.

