### 7.7.3. Objective 3: 2-Year Superiority

Superiority of coflex in conjunction surgical decompression relative to decompression alone will be evaluated by determining the Bayesian posterior probability that ( $CCS_{coflex+decomp.} - CCS_{decomp.} > 0$ ).  $H_0$  will be rejected in favor of  $H_a$  if the Bayesian posterior probability is at least equal to 0.95. The same prior distributions that were used in Objective 2 will be used in the evaluation of this posterior probability. The expected device group difference in Month 24 CCS between coflex® and decompression alone was evaluated based on results from an administrative analysis of the ongoing PAS being conducted in Germany. This study is also comparing coflex in conjunction with surgical decompression relative to surgical decompression alone. This analysis included 74

and 79 patients, respectively, in the coflex and decompression arms which comprised 85% and 81% of patients theoretically due for Month 24 follow-up. The device group difference in Month 24 overall success was 12.5% (95% CI -3.5% to 28.4%) based on a simplified CCS that incorporated reoperations, lumbar injections, and ODI improvements. Bayesian simulations demonstrate that with N=150 patients per group, there is 88% statistical power to demonstrate superiority. Type 1 error is controlled at <0.05 prior to prior and with prior on coflex® engaged. If the true difference is only 10%, then power is reduced to 73%.

It may be now noted that subsequent to the Bayesian design memo, the final results from this study have been published including a Month 24 CCS designed to be similar to the US IDE Study. Results demonstrated a 16.7% superiority margin (95% CI 3.1% to 30.2%) with coflex and decompression composite success observed in 58.4% (59/101) and 41.7% (43/103) patients, respectively.

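### Objective 2 power does not reproduce from its stated inputs (86.4%, not 89%), and Objective 3's type 1 error with the prior engaged stays below 0.05 only if the true coflex rate is about 0.65 or higher

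*Combined protocol and SAP*

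**What the plan says.** Section 7.7.2 gives a full set of inputs for Objective 2: a Beta(135.5, 69.5) prior for coflex, built from 135 successes among 204 patients in the IDE trial; a Jeffreys Beta(0.5, 0.5) prior for decompression; a margin of -0.10; and a 0.95 posterior threshold. For power, "it was assumed that the true success rate 0.662 for patients treated with coflex", with decompression at 0.642. For type 1 error, decompression is set 0.10 above coflex. The results are stated as "With N=150 patients per group, power was shown to be 89%; and type 1 error was shown to be 0.042 and 0.052", the first error figure without the informative prior and the second with it.

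Section 7.7.3 uses the same priors for Objective 3. It states that "there is 88% statistical power to demonstrate superiority" and that "If the true difference is only 10%, then power is reduced to 73" per cent. The synopsis ties the first of these to a 12.5-point difference, saying N=150 per group "will result in 88% statistical power to demonstrate superiority". Neither place names the coflex rate assumed. On error, 7.7.3 says "Type 1 error is controlled at <0.05 prior to prior", and says the same with the coflex prior engaged. The section also quotes the German study, with "composite success observed in 58.4% (59/101) and 41.7% (43/103) patients" for coflex and decompression.

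For Objective 1, by contrast, section 7.7.1 discounts the prior by 20% and reports error at a second true rate: "type 1 error is 0.040, still below 0.05, if the true success rate is 56% rather than 57" per cent. The documents do neither for Objectives 2 and 3. Section 7.7 refers to a separate simulation memo for details; it is not part of the file.

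**The concern.** There are two faults. First, the inputs in 7.7.2 are complete enough to recompute the operating characteristics, and the stated figures do not come out.

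Second, and more important, the Objective 3 claim of error below 0.05 has no condition on the true success rate. The IDE prior carries a weight of 135.5 + 69.5 = 205, more than the 150 coflex patients in the new study. If these patients do less well than the IDE patients, the prior pulls the coflex estimate up and nothing offsets this in the control arm. The plan itself allows for such a shortfall: the sites are new, the endpoint for Objectives 2 and 3 is modified from the IDE version, and Objective 4 exists to test for it.

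At stake is whether a 2-year non-inferiority or superiority conclusion rests on the new comparison or on the old single-arm data. The planned completers and tipping-point analyses address missing outcomes, not the prior, so they would not show the difference.

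**Working it through.** **Inputs** (sections 7.7.2 and 7.7.3): n = 150 per arm; threshold 0.95; margin δ = 0.10 for Objective 2 and 0 for Objective 3. With x₁ coflex and x₂ decompression successes, the posteriors are

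- π_C ~ Beta(135.5 + x₁, 69.5 + 150 − x₁)
- π_D ~ Beta(0.5 + x₂, 0.5 + 150 − x₂)

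**Formula.** The probability of declaring success at true rates (p_C, p_D) is

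Σ Σ Bin(x₁; 150, p_C) · Bin(x₂; 150, p_D) · 1{P(π_C − π_D > −δ | x₁, x₂) ≥ 0.95},

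summed over all 151 × 151 outcomes, with the inner probability found by numerical integration. No simulation error enters.

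**Check of the method on Objective 1**, with the stated Beta(82.1, 62.1) prior and coflex at 0.57: power is 82.2% and 64.6% (stated 83% and 65%). Type 1 error is 0.035 at 0.57 (stated 0.037) and 0.044 at 0.56 (stated 0.040). The method comes close to the plan's figures there.

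**Step 1: the stated figures for Objectives 2 and 3**

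| Quantity | True rates (coflex / control) | Recomputed | Stated |
|---|---|---|---|
| Obj 2 power | 0.662 / 0.642 | 86.4% | 89% |
| Obj 2 type 1, with prior | 0.662 / 0.762 | 0.033 | 0.052 |
| Obj 2 type 1, Jeffreys coflex prior | 0.662 / 0.762 | 0.052 | 0.042 |
| Obj 3 power, 12.5 points | 0.662 / 0.537 | 86.1% | 88% |
| Obj 3 power, 10 points | 0.662 / 0.562 | 69.8% | 73% |
| Obj 3 type 1, with prior | 0.662 / 0.662 | 0.035 | <0.05 |

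The gaps in power are 2.6, 1.9 and 3.2 points. The Objective 3 rows assume 0.662 carries over from Objective 2. A coflex rate of 0.655 would give 87.9% and 72.8%, close to the stated pair, but the documents do not mention it. The stated 0.052 with the prior equals the value computed without it, so the two labels may be reversed; even then 0.042 does not match 0.033.

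**Step 2: type 1 error with the prior, by true coflex rate.** For Objective 3 the control rate equals the coflex rate; for Objective 2 it is 0.10 higher.

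| True coflex rate | Obj 3 false superiority | Obj 2 false non-inferiority |
|---|---|---|
| 0.662 | 3.5% | 3.3% |
| 0.65 | 5.0% | 4.9% |
| 0.64 | 6.6% | 6.6% |
| 0.62 | 10.8% | 11.1% |
| 0.60 | 16.5% | 17.4% |
| 0.584 | 22.2% | 23.7% |

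The error crosses 0.05 at 0.650 for Objective 3 and 0.649 for Objective 2. With a Jeffreys coflex prior both errors stay between 4.7% and 5.3% for true rates from 0.55 to 0.70. The 0.584 row is the German coflex rate, used as a stress test and not as the expected rate.

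**Step 3: what this means in data.** Suppose 88 of 150 coflex patients (58.7%) succeed. The posterior mean becomes (135.5 + 88)/(205 + 150) = 223.5/355 = 63.0%, an upward shift of 4.3 points.

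- Superiority is then declared with control as high as 82/150 (54.7%). With a Jeffreys coflex prior, control would have to be 73/150 (48.7%) or lower.
- Non-inferiority is declared with control up to 98/150, against 89/150 under Jeffreys.
- If control also has 88/150, the posterior probability of superiority is 0.82 with the IDE prior and 0.50 with Jeffreys.

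**The case against.** The strongest replies are these.

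*The details sit in a memo that was reviewed.* The memo may tabulate error over true rates, and it may explain the power figures. This is why the cause is left open. It does not change what this document tells its reader.

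*The wrong input may be N, not the power.* With 165 per group at 0.662, power is 88.9%, 88.3% and 72.6%, which fits all three stated powers. That is a fair point against simply overwriting them. But it contradicts the stated N=150 and leaves the type 1 pair unmatched: the with-prior error for Objective 2 is still 0.032.

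*Other readings of the method.* A Beta(1, 1) control prior, as in the imputation formula of section 7.11.1, gives 87.0%; section 7.7.2 specifies Jeffreys. Treating the IDE data as random gives a type 1 error of 0.051 but power of 84.0%. Neither reproduces the full set.

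*The power gap has little practical effect.* After planned trimming, 186 × 0.95 and 220 × 0.80 leave about 176 per arm, and missing outcomes are imputed. At 172 per arm, power is 89.5%, 89.3% and 73.9%, before imputation noise. This stands, and is why the power gap alone would be minor.

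*Objective 4 is a warning in itself.* It tests coflex performance against the IDE trial with non-informative priors. At 88/150 its posterior is 0.79, so it fails; 95/150 is needed. At true rates of 0.584 and 0.60 it passes only 13% and 23% of the time. So a reader would have some signal. But Objective 4 does not gate Objectives 2 and 3, uses a slightly different endpoint, and does not qualify the error claim in 7.7.3.

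*Borrowing always has this property.* True, and section 7.1 argues for borrowing. The point is that the dependence should be shown.

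**Conclusion.** The concern holds. On the inputs in section 7.7.2, Objective 2 power is 86.4% rather than 89%, and neither stated type 1 error matches its label. Objective 3 power is 86.1% and 69.8% rather than 88% and 73%, if 0.662 is the coflex rate used. The cause cannot be settled without the memo.

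The Objective 3 statement of error below 0.05 with the prior engaged is correct at the design rate but fails once the common true rate drops below about 0.65, only 1.2 points under 0.662. By 0.60 the false-superiority rate is about one in six. Objective 2's single figure has the same limitation.

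These results assume 150 evaluable patients per arm, simple binomial outcomes without propensity-score weighting or imputation, and that the error without the prior refers to a Jeffreys coflex prior, a term the plan does not define.

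**What to change.** 1. Reconcile 89%, 88%, 73% and the 0.042/0.052 pair with the 0.95 rule and N=150, and state the coflex rate used for Objective 3. Unless the memo shows different inputs, restate power as about 86% for Objective 2 and 86% and 70% for Objective 3, in sections 7.7.2 and 7.7.3 and in the synopsis.
2. Replace the unconditional error claim for Objective 3, and supplement the single-point figure for Objective 2, with a table of type 1 error over true coflex rates from 0.55 to 0.70, including 0.584.
3. Pre-specify a sensitivity posterior with a Jeffreys coflex prior, reported beside the Objective 2 and 3 results, and for Objective 1 for consistency. Where the two disagree, describe the conclusion as dependent on the IDE prior.

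The cost is wording in the statistical section and synopsis, one table from existing simulation code, and one extra run per objective. Sample size and decision rule do not change. The drawback is that the stated figures look slightly less favourable.

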### 7.7.3. Objective 3: 2-Year Superiority

Superiority of coflex in conjunction surgical decompression relative to decompression alone will be evaluated by determining the Bayesian posterior probability that ( $CCS_{coflex+decomp.} - CCS_{decomp.} > 0$ ).  $H_0$  will be rejected in favor of  $H_a$  if the Bayesian posterior probability is at least equal to 0.95. The same prior distributions that were used in Objective 2 will be used in the evaluation of this posterior probability. The expected device group difference in Month 24 CCS between coflex® and decompression alone was evaluated based on results from an administrative analysis of the ongoing PAS being conducted in Germany. This study is also comparing coflex in conjunction with surgical decompression relative to surgical decompression alone. This analysis included 74

and 79 patients, respectively, in the coflex and decompression arms which comprised 85% and 81% of patients theoretically due for Month 24 follow-up. The device group difference in Month 24 overall success was 12.5% (95% CI -3.5% to 28.4%) based on a simplified CCS that incorporated reoperations, lumbar injections, and ODI improvements. Bayesian simulations demonstrate that with N=150 patients per group, there is 88% statistical power to demonstrate superiority. Type 1 error is controlled at <0.05 prior to prior and with prior on coflex® engaged. If the true difference is only 10%, then power is reduced to 73%.

It may be now noted that subsequent to the Bayesian design memo, the final results from this study have been published including a Month 24 CCS designed to be similar to the US IDE Study. Results demonstrated a 16.7% superiority margin (95% CI 3.1% to 30.2%) with coflex and decompression composite success observed in 58.4% (59/101) and 41.7% (43/103) patients, respectively.

#### **7.7.4. Objective 4: Real Conditions of Use**

Non-informative priors were assumed for the both comparisons groups, since IDE results cannot be used as the basis of an informative prior if the comparison is to be made to that same IDE trial. However, the Bayesian simulation R function was modified to reflect that it is known that exactly 135 successes were observed among 204 evaluable patients in the coflex IDE analysis set (see Simulation Report, Section 8.3). Otherwise, all other features of the Bayesian simulation were kept the same.

A design was identified that uses a non-inferiority margin of -0.1175 and a 0.95 posterior probability threshold. This design has an estimated type 1 error of 0.045 and power of about 80%. Other assumptions include expected success rates 0.662 in both groups when determining power and assuming that the Month 24 success rate in the PAS population is 0.10 smaller than in the IDE study population for evaluating type 1 error.

### **7.8. Alternative CCS Using Treadmill Test**

Objectives 1, 2 and 3 focus on comparisons between coflex® in conjunction with surgical decompression relative to decompression alone. A modified CCS will be assessed as a secondary endpoint for these objectives. For this modified CCS, the criterion that the Oswestry Disability Index (ODI) must improve by at least 15 points will be replaced by a criterion that more directly measures physical function. This endpoint (CCS-WDT) is a function of the maximum time a patient can walk on a treadmill (up to 15 minutes) before symptoms are too severe to continue. The specific treadmill success criterion will be an improvement in the total walking time from baseline to follow-up of at least 8 minutes. For patients with a baseline value that is >7 minutes, the follow-up walking test success criteria is the ability to achieve the maximum walking test time of 15 minutes. This allows patients with >7 minutes at baseline to achieve success. These definitions were developed using data from the ongoing German study of coflex® compared to decompression alone.

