### 3.3. Secondary Endpoints

- ODI change compared to baseline at 24 and 60 months as a continuous variables and in terms of achieving at least a 15 point improvement.
- Change in Visual Analog Scale (VAS) for low back pain (on the 100 mm scale) after 24 and 60 months compared to baseline as a continuous variables and in terms of achieving a 20 point improvement.
- Change in right and left leg pain using a Visual Analog Scale (VAS) 100 mm scale after 24 and 60 months compared to baseline as a continuous variable and in terms of achieving a 20 point improvement. A separate analysis will be performed to compare VAS scores for the “worst” legs.
- Change of Zurich Claudication Questionnaire (ZCQ) after 24 and 60 months compared to baseline:
  - Symptom severity (range 1-5)
  - Physical function (range 1-4)
  - Patient satisfaction (range 1-4, no baseline).
  - ZCQ Overall Success ( $\geq 2$  of 3 of the following)
    - Improvement in symptom severity  $\geq 0.5$
    - Improvement in physical function  $\geq 0.5$
    - Satisfied or somewhat satisfied as defined by a score of  $\leq 2.5$  points on the patient satisfaction domain.
  - ZCQ Overall Success components
- Maintenance or improvement in EQ-5D compared to baseline
- Change from baseline to Month 24 and Month 60 in maximum walking time from treadmill test as a continuous variable and in terms of achieving at least an 8 minute improvement or maximum time of 15 minutes.
- Change from baseline to Month 24 and Month 60 in time to symptoms from treadmill test as a continuous variable and in terms of achieving at least an 8 minute improvement or maximum time of 15 minutes.
- Neurological status (no new or worsening, persistent neurological deficit)
- Radiography Endpoints
  - Assessment of significant migration of the implant or the complete expulsion (significant is defined  $> 5$  mm).
  - Assessment of spinous process fracture.
  - Assessment of maintenance of foraminal height
  - Assessment of adjacent level disease determined by independent radiographic review
- Correlation of foraminal height changes to improvement of walking distance on a treadmill (after 24 and 60 months compared to baseline).

 Pratt RK et al., The Reliability of the Shuttle Walking Test, the Swiss Spinal Stenosis Questionnaire, the Oxford Spinal Stenosis Score and the Oswestry Disability Index in the Assessment of Patients with Lumbar Spinal Stenosis. Spine Vol. 27 (1) pp. 84-91.

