## 4. Subjects and Methods

### 4.1. Study Design

This is a prospective, non-randomized study with concurrently enrolled controls involving up to 20 centers in the US to assess the safety and effectiveness of the coflex® Interlaminar Technology for the treatment of at least moderate leg/buttocks/groin pain with or without low back pain in patients with moderate to severe spinal stenosis. Covariate balance will be achieved through a rigorous application of propensity score subclassification.

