### 4.3. Inclusion Criteria

1. Radiographic confirmation of at least moderate lumbar stenosis, which narrows the central spinal canal at one or two contiguous levels from L1-L5 that require surgical decompression. Moderate stenosis is defined as > 25% reduction of the antero-posterior dimension compared to the next adjacent normal level, with nerve root crowding compared to the normal level, as determined by the investigator on CT Scan or MRI.\* The patient may have, but is not required to have for inclusion in the study:
  - a. Facet hypertrophy and subarticular recess stenosis at the affected level(s);
  - b. Foraminal stenosis at the affected level(s);
  - c. Up to stable Grade I degenerative spondylolisthesis (Meyerding classification) or equivalent retrolisthesis as determined by flexion/extension X ray:
    - i. For single level disease, there may be up to a stable Grade I spondylolisthesis or equivalent retrolisthesis at the affected level as determined on flexion/extension films by the investigator.
    - ii. For two level disease, there may be up to a stable Grade I spondylolisthesis or equivalent retrolisthesis at only one of the two contiguous affected levels as determined on flexion/extension films by the investigator. Patients with up to stable Grade I spondylolisthesis at two contiguous levels are excluded, but patients with up to Grade I stable spondylolisthesis at one level and equivalent retrolisthesis at the adjacent level may be included.
  - d. Mild lumbar scoliosis (Cobb angle up to 25°)
2. Radiographic confirmation of no angular or translatory instability of the spine (instability as defined by White & Panjabi: Sagittal plane translation >4.5mm or 15% or sagittal plane

rotation >15° at L1-L2, L2-L3, and L3-L4; >20° at L4-L5 based on standing flexion/extension X-rays)

3. VAS back pain score of at least 50 mm on a 100 mm scale.
4. Neurogenic claudication as defined by leg/buttocks or groin pain that can be relieved by flexion such as sitting in a chair.
5. Patient has undergone at least one epidural injection at any prior time point, AND at least 6 months of prior conservative care without adequate and sustained symptom relief.
6. Skeletally mature
7. Oswestry Low Back Pain Disability Questionnaire score of at least 20/50 (40%).
8. Appropriate candidate for treatment using posterior surgical approach.

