### **5.2.1. Walking Distance Test on a Treadmill**

Patients will perform a walking distance test on a treadmill at screening (visit 1) and post-operatively. It will be assessed if a patient can walk on the 0° ramp incline at a speed of 1.2 miles/hour for 15 minutes (according to the publication by Deen).

Also assessed will be time to first symptoms, time to severe symptoms and nature of symptoms (leg weakness, leg pain, back pain, or generalized fatigue, other). A time of zero will be recorded when symptoms were present at onset. The examination will be stopped after 15 minutes or at the onset of severe symptoms.

**Definition of severe symptoms is:** The level of discomfort that would make patients stop their activities in usual life situations. Patients will be instructed to walk with an upright posture. They are not permitted to lean forward or to hold onto the handrails during examination.

It is assumed that patients with additional back pain will have more problems in managing the complete walking distance and therefore may stop the walking distance test before the endpoint at 15 min.

The investigator has to check whether the patient shows any medical contraindication against the performance of a walking distance test (Deen 1995, p 28).

If the patient is not able to perform the walking distance test at any of the clinical visits it does not lead to an exclusion of the study.

In summary, the primary endpoints from the treadmill test will be:

- Change from baseline to Month 24 and Month 60 in maximum walking time from treadmill test as a continuous variable and in terms of achieving at least an 8 minute improvement or maximum time of 15 minutes.
- Change from baseline to Month 24 and Month 60 in time to symptoms from treadmill test as a continuous variable and in terms of achieving at least an 8 minute improvement or maximum time of 15 minutes.

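### Treadmill and leg-pain responder endpoints ignore the baseline value: a patient at 15 minutes at baseline can meet the treadmill criterion with no gain, and a leg below 20 mm can never meet the 20-point criterion

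*Combined protocol and SAP*

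**What the plan says.** **Treadmill.** Section 5.2.1 caps the test: "The examination will be stopped after 15 minutes or at the onset of severe symptoms". Section 7.8 defines the treadmill component that replaces the ODI criterion in CCS-WDT: "The specific treadmill success criterion will be an improvement in the total walking time from baseline to follow-up of at least 8 minutes". It then makes an exception when the baseline time exceeds 7 minutes. In that case "the follow-up walking test success criteria is the ability to achieve the maximum walking test time of 15 minutes". The stated purpose is to make success attainable for these patients. The synopsis has the same exception for Month 24. The stand-alone responder endpoints for maximum walking time and for time to symptoms (synopsis, 3.3, 5.2, 5.2.1) use "at least an 8 minute improvement or maximum time of 15 minutes". No text deals with a baseline of 15 minutes.

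**Leg pain.** Section 3.3 lists "Change in right and left leg pain using a Visual Analog Scale (VAS) 100 mm scale after 24 and 60 months compared to baseline", analysed both as a continuous variable and as a 20-point improvement; 5.2.2 does the same. The synopsis adds a worst-leg endpoint in both forms, and 3.3 adds a separate worst-leg comparison. Sections 5.2 and 5.2.2 do not mention the worst leg. No leg responder analysis has a baseline minimum.

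**Entry.** Section 4.3 requires "VAS back pain score of at least 50 mm on a 100 mm scale", ODI of at least 40%, at least moderate stenosis, and claudication defined qualitatively, for which buttock or groin pain is enough. Exclusion 12 in 4.4 removes only patients with purely axial pain. Section 4.1, in contrast, describes the population as having "at least moderate leg/buttocks/groin pain with or without low back pain in patients with moderate to severe spinal stenosis".

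**The concern.** A responder endpoint should separate patients who improved from those who did not. Here some patients can be counted as treadmill responders with no improvement, and some legs cannot be counted as responders whatever happens. The responder percentages then partly reflect who was enrolled.

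That matters more than usual here because the arms are not randomised. Each site enrols only one arm (4.6), and comparability rests on the propensity score. The variable list in 7.17.2 has ODI, ZCQ physical function and maximum leg VAS but not baseline treadmill time, so nothing directly balances the share of patients at the ceiling. CCS-WDT is the alternative composite for Objectives 1, 2 and 3 and is presented as the more direct measure of physical function.

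An example: a patient with ODI 44 and back pain 70 mm walks the full 15 minutes before and after surgery, and ODI does not change. The patient fails the primary CCS on ODI but meets the treadmill component of CCS-WDT.

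**Working it through.** **1. The plan's cut-off.** The ceiling is 15 minutes (5.2.1) and the required gain is 8 minutes (7.8). 15 − 8 = 7, which reproduces the plan's cut of 7 minutes. Above it, an 8-minute gain is impossible, so the exception is needed.

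**2. Gain required under the rule.** It is 8 minutes if baseline ≤ 7, otherwise 15 − baseline.

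| Baseline (min) | Gain required (min) |
|---|---|
| 0 to 7 | 8 |
| 8 | 7 |
| 10 | 5 |
| 12 | 3 |
| 14 | 1 |
| 15 | 0 |

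The requirement reaches zero at 15 minutes. Such patients are eligible, since no criterion in 4.3 or 4.4 refers to walking time. At the test speed of 1.2 miles/hour, 15 minutes is 1.2 × 0.25 = 0.3 miles.

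**3. Leg pain.** The largest possible improvement equals the baseline VAS. Below 20 mm it is less than 20, so the leg is a certain non-responder. If a share g of legs starts below 20 mm, the responder rate cannot exceed 1 − g: 90%, 80% and 70% for assumed g of 10%, 20% and 30%.

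**4. Dilution (assumed shares).** Let a share f of each arm be at the ceiling, with equal success in both arms among them, and let the others differ by 12.5 points. That figure is the difference in 7.7.3, which comes from a simplified ODI-based composite, so it serves only as a scale. Observed difference = (1 − f) × 12.5:

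- f = 10%: 0.9 × 12.5 = 11.25
- f = 20%: 0.8 × 12.5 = 10.0
- f = 30%: 0.7 × 12.5 = 8.75

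**5. Spurious difference (assumed shares and rates).** With no treatment effect, the spurious difference is the arm difference in ceiling share × (success at the ceiling − success off it).

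- 10-point imbalance, 0.85 at the ceiling and 0.54 off it: 0.10 × 0.31 = 3.1 points
- 20-point imbalance, same rates: 0.20 × 0.31 = 6.2 points
- Upper end for a 10-point imbalance, every ceiling patient a success and 0.50 off the ceiling: 0.10 × 0.50 = 5 points

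**The case against.** Five arguments can be made for leaving the plan as it is.

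- **Ceiling patients are not automatic CCS-WDT successes.** This stands. A reader might infer that they are, but they must reach 15 minutes again and meet the other components: no index-level surgery, no disqualifying injection and, at Month 24, no serious and definitely related event. The 5-point figure, which assumes 100% composite success at the ceiling, is therefore an upper end. These components could also differ by arm among ceiling patients, so the dilution figures depend on assuming that they do not.
- **Leg pain is already handled.** This stands in part. The worst-leg endpoint in the synopsis answers one-sided pain, and continuous change is kept throughout. What remains is a worst leg below 20 mm (for example with buttock or groin pain only), the denominators of the right and left leg tables, and the missing statement that the worst leg is fixed at baseline.
- **No study conclusion turns on these endpoints.** This stands. Section 7.9 plans descriptive summaries with 95% intervals, and no margin, threshold or power is attached to CCS-WDT. A reader might set the spurious difference against the 10-point margin of Objective 2, but that margin belongs to the ODI-based primary composite.
- **The ceiling share may be small.** This may be so. Patients must have claudication and stenosis, and they walk upright without handrails. Section 7.8 says the definitions were developed on data from the German study. The documents give no baseline distribution, so the share is unknown in either direction.
- **Propensity adjustment deals with imbalance.** Only indirectly. ODI and ZCQ physical function are partial stand-ins for walking time, which is not listed.

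**Conclusion.** The point holds as a limited defect in secondary endpoints. From the text alone, a patient at 15 minutes at baseline meets the treadmill component of CCS-WDT, and the stand-alone maximum-time responder endpoint, with no improvement by reaching 15 minutes again; the time-to-symptoms endpoint carries the same wording. A leg below 20 mm cannot meet the 20-point criterion, and the entry criteria prevent neither case.

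The size cannot be computed from the documents. On the assumed shares and rates above, dilution takes 12.5 points to between 11.3 and 8.8. A 10-point imbalance in ceiling share creates about 3 points, and at most about 5. The documents do not support reading this as a threat to the primary hypotheses. Nor do they show that the exception above 7 minutes is a mistake: it solves the problem it was written for and leaves the zero-gain case open.

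**What to change.** 1. **Treadmill.** In the synopsis, 3.3, 5.2 and 5.2.1, calculate the maximum-time and time-to-symptoms responder percentages among patients below 15 minutes at baseline on that measure. Show the number of ceiling patients and their maintenance rate by arm. In 7.8, report CCS-WDT also excluding, or stratified by, a baseline of 15 minutes. Do not substitute the ODI criterion for these patients: the composite would then measure different things depending on baseline, and its purpose is to replace ODI.
2. **Leg pain.** Calculate the 20-point responder endpoint only for legs with a baseline of at least 20 mm. Make the worst leg, fixed at baseline, the lead leg analysis, and state this consistently in the synopsis, 3.3, 5.2 and 5.2.2. Keep continuous changes for all patients.
3. **Population.** Reconcile the description in 4.1 with the criteria in 4.3. They differ on whether back pain is required and on whether leg, buttock or groin pain has a minimum severity.

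The data are already collected. The cost is slightly smaller responder denominators, some programming, and minor edits to protocol and SAP text; under 9.1 protocol amendments go to the IRB. The denominators should be fixed before outcomes are unblinded, so that the choice cannot look data-driven.
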